10 minutes after receiving the Secretin or placebo, the attending surgeon will examine the anastomosis or repaired cut edge of the pancreas to determine if leakage of pancreatic fluid is noted, leak location(s), type (side branch/main duct), color of the fluid and whether any further intervention was performed in an effort to close the leak. Specifics of operative intervention will be documented. The patient will then undergo standard surgical closure of the abdomen.

As is standard of care at DHMC, surgical drains will be placed adjacent to the anastomosis and drain amylase output will be checked on POD #1 through POD#5. Pancreatic leak is defined according to the International Study Group of Pancreatic Fistula (ISGPF) definition as a clinically relevant postoperative pancreatic fistula is now redefined as a drain output of any measurable volume of fluid with an amylase level >3 times the upper limit of institutional normal serum amylase activity, associated with a clinically relevant development/condition related directly to the postoperative pancreatic fistula. Randomization assignments will be revealed once the patient has been discharged from the hospital following their initial surgical intervention. A follow-up visit with the patient two weeks following discharge, will evaluate for any evidence of ongoing pancreatic duct leak.

The patient will also be followed for thirty (30) days after secretin/placebo administration by the research team to assess for a pancreatic leak and sequelae of a leak, - intra abdominal deep soft tissue infection, surgical site infection, hemorrhage, IR (interventional radiology) drain placement, or reoperation. This will be accomplished by telephone and/or by chart review Patients discharge date will be followed for the study. If no secretin/placebo is administered, the patient will not be followed on the study.

If any of the above are noted during the 30 days following secretin/placebo administration the following will be used to assess causality:

Causality

The following 4-point scale will be used for rating the causal relationship of the AE to the investigational product:

Unrelated: Clearly and incontrovertibly due to extraneous causes, and does not meet criteria listed under unlikely, possible, or probable.

- Unlikely:** Does not follow a reasonable temporal sequence from administration. May have been produced by the patient's clinical state or by environmental factors or other therapies administered.

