- Possible:** Follows as reasonable temporal sequence from administration. May have been produced by the patient's clinical state or by environmental factors or other therapies administered.
- Probable:** Clear-cut temporal association with improvement or cessation of test drug or reduction in dose. Reappears upon re-challenge. Follows a known pattern or response to test drug.

The primary outcome of interest will be the presence of pancreatic leaks based on the amount of drain amylase on or after POD#3. Secondary outcomes will include: 1) technical interventions intraoperatively directed to leak closure or manipulation of the anastomosis following Secretin or placebo stimulation 2) length of stay as a surrogate to complication severity after pancreatic surgery.

Patient demographics, risk factors, operative technique, randomization assignment and outcome data will be recorded on standard case report forms – **See Case Report Forms in Appendix**. Data will be stored in an encrypted hard-drive by a single agent ([name]) who is the only researcher who has access to the randomization data.

5. Inclusion/Exclusion Criteria:

Please provide detailed description of inclusion and exclusion criteria. If a formal protocol for the study exists, page references to the protocol are acceptable.

Inclusion criteria:

1. Scheduled for pancreatic surgery requiring pancreatic resection at DHMC
2. Age greater than 18 years old
3. Ability to provide written informed consent

Exclusion criteria:

1. Inability to provide written informed consent
2. Current ongoing acute pancreatitis
3. Pregnant or nursing mothers
4. Any medical condition which in the judgment of the Investigator renders participation in this study medically inadvisable.
5. Participation in an investigational clinical study for a drug or medical device within 30 days prior to Visit 1.
6. [Any known allergy to methylene blue.](#)

6. Financial Considerations:

Disclosure of financial impact on the participant is critical to informed consent. Insurance cannot be billed for research-related services outside the standard of care or paid for by the funding agency for

the study. The department, the study or the participant may be responsible for payment for research-related services. Participants should know which tests, visits, or procedures will be billed to them or their insurance and which ones will be paid by the funding agency for the study or the department.

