a) *List tests, visits, and procedures performed for only research purposes. These services are outside the standard of care. They would not be performed if the individual were not a research participant, and may not be billed to a health insurance plan.*

Note: 6a information must also be in "How is this different . . ." section of the consent form.

The administration of Secretin or placebo is for research purposes only and will not be billed to the patient. Drain placement, drain amylase measurement and the two week follow-up visit are per standard of care and will be billed directly to the patient.

b) *List the tests, visits, and procedures that may be standard care, but for which the funding agency for the study is paying.*

None

c) *Will the funding agency for the study be responsible for the above costs? Yes No
If No, describe who will be responsible (i.e., department or participant).*

Secretin will be supplied by ChiRhoClin, Inc and saline placebo will be supplied by the Section of Gastroenterology and Hepatology out of research funds maintained by the primary investigators. No additional tests, visits, or procedures will be performed for research purposes only.

PLEASE ENCLOSE THE DHMC BILLING GRID/PLAN. Also enclose the schedule of events or table listing all procedures from the sponsor protocol.

7. Statistical Methods and Review Statement:

a) *Specify the primary endpoint, as well as other endpoint(s).*

Primary Objective:

1. Pancreatic leak as defined by the ISGPF definition of post-operative pancreatic leaks

Secondary Objective:

1. Assess whether intervention is performed intra-operatively on the pancreatic anastomosis following Secretin or placebo injection.
2. Assess degree to which leakage severity, as a complication, increases length of stay.

b) *State the statistical analysis plan, including all hypothesis tests (e.g., t-test, chi-square), and estimation methods related to the primary endpoint. If a formal protocol for the study exists, page references to the protocol are acceptable.*

For the analysis of the primary endpoint, a categorical variable, we will use a two-tailed Fisher's Exact test to determine a p-value. We will then be able to calculate an absolute and relative risk reduction. We will also evaluate this variable using a student's t-test for means of amylase levels in the drain fluid. We will plan on performing univariate analysis of all of the potentially contributing variables outlined in the

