CRF, and then building a multivariable logistic regression model using the categorical variable of drain amylase >3x the upper limit of normal. The data from the multivariate regression will be reported as Odds Ratios.

The secondary outcomes are both categorical and continuous variables and thus we will use the Fisher's Exact test as well as the two-tailed student's t-test. A multivariable analysis is not planned for evaluating the secondary variable.

Randomization will occur in a block format of 5 and will be generated by the primary investigators.

c) Justify the sample size, using the concepts of power, type I error, and effect size if applicable. If a formal protocol for the study exists, page references to the protocol are acceptable.

A clinically significant absolute decrease of 15% (20% to 5%) in the pancreatic duct leak rate. Based on these estimates and a two-tailed test comparing proportions using the statistical calculator (<http://homepage.stat.uiowa.edu/~rlenth/Power>), we project an estimated sample size of **176 participants (88 per arm)** to demonstrate an absolute 15% reduction in the leak rate with 80% power at a two-sided alpha level of 0.05.

8. Data and Safety Monitoring:

Describe plans for data and safety monitoring to ensure the safety of subjects and the quality of the data. As described in federal guidance "... a variety of types of monitoring may be anticipated depending on the nature, size, and complexity of the trial. In many cases, the principal investigator would be expected to perform the monitoring function." This plan should include monitoring to determine:

The progress of the trial, including periodic assessments of data quality and timeliness, participant recruitment, accrual and retention, participant risk versus benefit, and other factors that can affect study outcome. Monitoring should also consider factors external to the study when interpreting the data, such as scientific or therapeutic developments that may have an impact on the safety of the participants or the ethics of the study.

Note: This section does not request information related to sponsor study monitor visits. This section requires a description of an adequate data and safety monitoring plan.

Interim analysis will be performed once 50% (88) patients have been enrolled. If more than 66% of cases of duct leak are in a particular study group, a formal comparison between groups will be performed with the use of a two-sided stopping boundary of 0.005%.

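### Section 7b's two supportive analyses (a t-test on mean drain amylase and a logistic model built from CRF variables) would be better as one named log-scale comparison and one small pre-specified model; minor, and the primary Fisher test and sample size are unaffected.

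*Combined protocol and SAP*

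**What the plan says.** Section 7b of the combined protocol and SAP analyses the primary endpoint with a two-tailed Fisher's exact test. It then adds two further analyses.

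- **Continuous amylase.** The same variable is also to be evaluated with a Student's "t-test for means of amylase levels in the drain fluid". No scale, transformation, day or per-patient summary is given. Section 4 says "drain amylase output will be checked on POD #1 through POD#5" and defines the primary outcome as the "presence of pancreatic leaks based on the amount of drain amylase on or after POD#3".
- **Regression.** Candidates come from the case report form (CRF), and each is looked at singly to begin with: "We will plan on performing univariate analysis of all of the potentially contributing variables outlined in the" form. After that step the plan is "building a multivariable logistic regression model using the categorical variable of drain amylase >3x the upper limit of normal", with results given as odds ratios. No covariate list, entry rule or limit on model size appears. The CRF appendix was not supplied for this review.

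Section 4 also gives a leak definition that requires more than the amylase threshold: the raised amylase must be "associated with a clinically relevant development/condition related directly to the postoperative pancreatic fistula". Section 7c sizes the trial on this effect: "A clinically significant absolute decrease of 15% (20% to 5%) in the pancreatic duct leak rate".

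**The concern.** Drain amylase after pancreatic resection is plausibly a mixture of low values in most patients and very high values in a few. On the raw scale a few leaking patients then drive the mean and the standard deviation, and the t-test loses power. With three eligible values per patient and none named, the comparison is also not fixed before the data are seen.

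The regression has few events to work with, and the plan does not say which of the CRF variables enter it. Section 4 says the CRF records operative technique and outcome data as well as demographics and risk factors. Nothing in section 7b therefore keeps out variables that arise after the infusion, such as a repair prompted by it. Its event, amylase above three times the upper limit, is also not the section 4 definition.

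At stake is the usefulness of the supporting evidence. The primary conclusion is not.

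**Working it through.** **1. The plan's own figure.** Inputs from section 7c: 20% vs 5%, two-sided alpha 0.05, power 80%.

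n = [1.960·√(2·0.125·0.875) + 0.842·√(0.20·0.80 + 0.05·0.95)]² / 0.15² = 75.1.

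With continuity correction: (75.1/4)·[1 + √(1 + 4/(75.1·0.15))]² = 87.9, so 88 per arm and 176 in total. This matches. Exact power of the Fisher test at 88 per arm is 83.8%. Nothing below changes either figure.

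**2. Values available per patient.** Scheduled POD1-5, window from POD3: POD3, POD4 and POD5, so up to three.

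**3. Raw versus log scale.** The documents give no amylase distribution, so these are assumptions.

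*Mixture model:* 88 per arm; leaks 20% vs 5%; medians 30, 60 or 100 without a leak and 1,000, 2,000 or 5,000 with one; log-SD 0.8, 1.15 or 1.5; within-patient correlation 0.7; 27 settings. The value compared is the POD3-5 maximum. Ranges are over repeated simulation runs.

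| | Raw t | Log t |
|---|---|---|
| Power | 25-71% | 30-81% |
| Non-significant when Fisher is significant (median) | 40-42% | 30% |

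The log scale gains a median of about 10 points, range roughly -4 to +28. In 2 of 27 settings the raw test is equal or better.

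*Single log-normal model, equal log-SD:* threshold exceeded by 20% vs 5%, so the standardised shift is 1.645 - 0.842 = 0.80. Log-scale power is about 99.9%. Raw-scale power is 99.8%, 97.8%, 87.5%, 67.9% and 48.9% at log-SD 0.5, 1.0, 1.5, 2.0 and 2.5.

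Both models agree on direction. They disagree widely on size.

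**4. Validity of the raw test.** With equal 20% leak rates, its type I error at any one value is 3-5% under the mixture. It is not inflated.

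**5. Undetectable values.** With an assumed assay limit of 5 to 30, setting them to half the limit changes power by at most 3 points and the ratio by about 1%.

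**6. Events for the logistic model.** 88 × 0.20 + 88 × 0.05 = 17.6 + 4.4 = 22. If both arms had 20%, 176 × 0.20 = 35. At 10 events per parameter this supports 22/10, about 2 terms (35/10, about 3). Treatment plus procedure type uses 2, or 22/2 = 11 events each. If amylase alone defines the event, the count may be higher.

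**7. If univariate results choose the covariates.** Assume 5, 10 or 20 null candidates, kept at p<0.10. At least one false risk factor reaches p<0.05 in the final model in 19%, 35% or 57% of simulated trials at 22 events (20%, 35% or 55% at 44). One pre-specified null covariate gives 4-5%. The secretin odds ratio moves by at most 0.005.

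**The case against.** The strongest reply is that little depends on this. The analyses sit beside an unaffected primary test, the raw t-test is valid, and screening barely moves the treatment odds ratio. That stands and is why the point is minor. It does not remove the case for a better method that costs only wording, and section 7b does not itself label these analyses supportive.

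The magnitudes are assumed. This also stands: step 3 supports the direction under right skew, and no single figure belongs to this trial.

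Several stronger readings are tempting and are not supported by the documents:

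- *That covariates are selected by univariate p-value.* The text puts univariate analysis before model building, and selection is the natural inference, but it is not stated. The candidate count is unknown, so the step 7 percentages are illustrations.
- *That the type I error is inflated.* Reporting the most favourable of POD3, POD4, POD5 and the maximum would give about 6-10% (raw) or 6-11% (log). Nothing suggests that this is planned.
- *That early drain removal biases the comparison.* The documents describe checks through POD5 and no early removal. Carrying POD1-2 values forward as the main rule would also bring in values from outside the window. With 50% of non-leak drains assumed removed and early values assumed three times higher, that rule left the log scale no better than raw in 6 or 7 of 27 settings. It belongs in a sensitivity analysis only.

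Two limits of the remedy are fair. A POD3-5 maximum closes an open-ended window, although it covers every scheduled measurement. And the model cannot simply adopt the primary definition until the section 4 statements agree.

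**Conclusion.** The point holds as a minor improvement to two supportive analyses. From the text alone, the t-test has no named scale or per-patient value, the logistic model has no entry rule in the text supplied, and its event differs from the section 4 leak definition. These need no distributional assumption. The event count of about 22 rests on section 7c's rates applying to the modelled event.

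The gain from the log scale, a median of about 10 points and roughly -4 to +28, rests wholly on the assumed mixtures. It would be negligible if amylase is only mildly skewed. A reader might infer that the planned t-test is invalid or that the trial's main result is in doubt. Neither follows: the raw test keeps its type I error, and the Fisher test and 176 patients are untouched. Either amylase test can also be non-significant when Fisher is significant, which is why the result should be labelled supportive.

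**What to change.** In section 7b:

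1. Replace the t-test with a comparison of log-transformed drain amylase at one named value, the maximum scheduled value from POD3 to POD5. Report a geometric-mean ratio with 95% CI, labelled supportive. Set undetectable values to half the assay's lower limit. Report per arm how many patients have no value in the window, and use any imputation, such as the last earlier value, as a sensitivity analysis only.
2. Replace the model building with one pre-specified logistic model of treatment plus procedure type (pancreaticoduodenectomy vs distal, the two named in the Abstract). State that only variables fixed before the infusion may enter, and label all other risk-factor odds ratios exploratory.
3. Reconcile the amylase-only event in section 7b with the section 4 definition, which also requires a clinically relevant condition. Use the reconciled primary definition in the model.

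Leave the Fisher test and sample size as they are.

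The cost is SAP wording, with no new data. The downsides are fewer risk-factor odds ratios, an amylase result on a ratio scale, and up to about 4 points less power for the log-scale test if leak/non-leak separation and spread are small.

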C) This would be a randomized, double-blind, placebo controlled trial. 1/2 of the patients would receive intra-operative secretin, the other half would receive saline placebo. Both the surgeon and patient would be blinded to the randomization assignment. The advantage of giving secretin would be that it may allow for the identification of a leak intra-operatively and subsequently allow for repair if the leak was identified prior to abdominal wall closure. While the safety profile of the drug is excellent, receiving the medication could theoretically cause an increased intraductal pressure which may cause a leak when one was not already present.

D) Human subjects are needed to evaluate intra-operative, intravenous secretin in patients undergoing pancreatic duct resection.

4. Design, procedures, materials and methods:

Use a level of detail similar to what would be used when submitting an article for publication in a peer reviewed journal. Explain the study procedures, data collection, and analysis process. Please define terms and explain concepts which might be confusing to reviewers who are not expert in the area of the study. If a formal protocol for the study exists, page references to the protocol are acceptable.

This study design is a prospective, double-blind, randomized-controlled trial. We will enroll patients in our institution undergoing pancreatic resection to receive either 1) one dose weight-based Secretin to be given once the closure of the pancreatic resection margin is complete 2) saline placebo.

Consent and basic demographics will be garnered by the physician in an office visit once the surgery has been scheduled and consent for the surgery is being obtained. The consent will be validated by the treating surgeon in the pre-procedure area on the day of the surgery.

The patient will undergo the scheduled surgery. Once the pancreatic anastomosis has been deemed acceptable by the attending physician, but prior to abdominal closure, the patient will be randomized to receive either Secretin (0.2 mcg/kg) or saline placebo. The attending surgeon will be blinded to this assignment.

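### Section 7b does not limit the logistic model to variables fixed before the infusion; if leak seen or further repair enters a model with arm, the arm odds ratio is no longer a randomised comparison

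*Combined protocol and SAP*

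**What the plan says.** Section 7b tests the primary endpoint with an unadjusted two-tailed Fisher's exact test, with absolute and relative risk reductions. It then adds a model in two steps. The first is a screen of candidates taken from the case report form (CRF): "We will plan on performing univariate analysis of all of the potentially contributing variables outlined in the". The second step, which follows directly in the same sentence, is the model itself: "CRF, and then building a multivariable logistic regression model using the categorical variable of drain amylase >3x the upper limit of normal". On reporting it says "The data from the multivariate regression will be reported as Odds Ratios". It gives no covariate list and no selection rule. It does not say whether arm is always in the model, and it places no limit on when a candidate variable must have been measured.

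Section 4 describes what is recorded after the infusion: "10 minutes after receiving the Secretin or placebo, the attending surgeon will examine the anastomosis or repaired cut edge of the pancreas". The surgeon notes whether fluid is leaking, where, from which type of duct and of what colour, and "whether any further intervention was performed in an effort to close the leak". It adds: "Specifics of operative intervention will be documented". On the CRF it says: "Patient demographics, risk factors, operative technique, randomization assignment and outcome data will be recorded on standard case report forms". Section 4 also makes post-infusion technical intervention the first secondary outcome, and section 7a repeats it.

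**The concern.** Section 3B states the intended mechanism: secretin makes a leak visible, and the surgeon then closes it. Leak seen and further repair are therefore consequences of arm. They are also markers of patients who had an intra-operative leak and so are more likely to leak later. A model that holds such a variable fixed compares groups that randomisation did not make alike. Among patients with no further repair, secretin patients have mostly been cleared of leaks, while placebo patients still include most of the undetected ones. Secretin then looks protective even if the repairs achieve nothing. A univariate screen makes entry likely, because such a variable predicts leak.

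The same mechanism can hide harm. Section 3C concedes that secretin "could theoretically cause an increased intraductal pressure which may cause a leak when one was not already present". Leaks provoked in this way are the ones the surgeon would see and treat, so adjusting for the repair credits the harm to the repair and not to the arm.

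**Working it through.** **Design figure.** For 20% v 5%, two-sided alpha 0.05 and 80% power, the usual two-proportion formula gives

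n = [1.960·√(2 × 0.125 × 0.875) + 0.842·√(0.16 + 0.0475)]² / 0.15² ≈ 75.1, so 76 per arm.

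With the continuity correction, n′ = (75.1/4)·[1 + √(1 + 4/(75.1 × 0.15))]² ≈ 88 per arm. This reproduces the plan's 176. The simulations below use 88 per arm.

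**Assumptions, because the documents give none.**
- 20% of patients in each arm have an intra-operative leak.
- 80% (secretin) v 10% (placebo) of these leaks get a further repair; 50% on secretin is also tried.
- 5% of leak-free patients get one.
- Repairs do nothing, so the true odds ratio is 1.
- Loose link: 60% of intra-operative leaks and 10% of other patients leak postoperatively. Perfect link: 100% and 0%. Either way the postoperative rate is 20% (loose: 0.20 × 0.60 + 0.80 × 0.10 = 0.20).

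**Worked case: no effect, loose link, 80% v 10% repaired.** Shares are of each arm.

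| Stratum | Arm | Share in stratum | Later leak | Risk |
|---|---|---|---|---|
| No further repair | Secretin | 0.04 + 0.76 = 0.80 | 0.024 + 0.076 = 0.100 | 12.5% |
| No further repair | Placebo | 0.18 + 0.76 = 0.94 | 0.108 + 0.076 = 0.184 | 19.6% |
| Further repair | Secretin | 0.16 + 0.04 = 0.20 | 0.096 + 0.004 = 0.100 | 50.0% |
| Further repair | Placebo | 0.02 + 0.04 = 0.06 | 0.012 + 0.004 = 0.016 | 26.7% |

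- Overall: 0.200 v 0.200, odds ratio 1.00.
- No further repair: (0.100/0.700)/(0.184/0.756) = 0.59.
- Further repair: (0.100/0.100)/(0.016/0.044) = 2.75.
- Mantel-Haenszel summary: [0.100 × 0.756/1.74 + 0.100 × 0.044/0.26] / [0.700 × 0.184/1.74 + 0.100 × 0.016/0.26] = 0.0604/0.0802 = 0.75.

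A true null has become an apparent benefit.

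**Simulated trials.** Repair enters the model if it passes a univariate p<0.05 screen (assumed; 7b gives no rule). A significant result means a Wald |z| above 1.96. There is no true effect, so false benefit should be near 2.5%.

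| Link | Leaks repaired, secretin v placebo | Median model odds ratio | False significant benefit |
|---|---|---|---|
| Loose | 50% v 10% | 0.92 | 4% |
| Loose | 80% v 10% | 0.77 | 7% |
| Perfect | 50% v 10% | 0.78 | 9% |
| Perfect | 80% v 10% | 0.46 | 35% |

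The unadjusted analysis gives 2–3%.

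**Harm.** Suppose secretin also provokes a leak in 15% of leak-free patients, all seen and none fixed, and 50% of the other leaks are found. Intra-operative leaks on secretin are then 0.20 + 0.80 × 0.15 = 0.32.
- Perfect link: 32% v 20%; unadjusted odds ratio (0.32/0.68)/(0.20/0.80) = 1.88; model about 1.0. Significant harm appears in 44% of trials unadjusted and about 3% in the model.
- Loose link: 0.32 × 0.60 + 0.68 × 0.10 = 26% v 20%; unadjusted (0.26/0.74)/(0.20/0.80) = 1.41; model about 1.0.

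**Benefit near the design effect.** If 90% of leaks are found and repairs are 85% effective, the odds ratio is about 0.2 with or without the screened model. Repair passes the screen in only about 3% of trials.

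**Second check, adjusting for leak seen instead of repair, under separate assumptions.** With no effect, the odds ratio moves from 1.00 to 0.89 (detection 60% v 30%), 0.78 (80% v 20%), or 0.43 (90% v 10% with a strong link). With 10%, 15% and 20% provoked leaks, 1.26, 1.41 and 1.56 become 0.88, 0.94 and 0.99. The direction is the same throughout these no-effect and harm cases.

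**The case against.** - **The CRF cannot be seen.** It is an appendix outside the available text. It may list contributing factors apart from intra-operative findings, and Section 4 does name outcome data as a separate class from risk factors and technique. This stands as a limit, and the point has to be conditional. But operative technique could include a re-repair, and no sentence in the available text excludes one.
- **A secretin odds ratio is not promised.** A reader might infer that 7b commits to reporting an adjusted treatment effect. It does not. It never names arm as a model term, and the text also fits a risk-factor model. Against that, assignment is recorded on the CRF, and the model is described within the primary-endpoint analysis with no exploratory label.
- **The large figures need a strong assumption.** A reader might take 0.46 and 35% as the expected bias. Those figures require every unrepaired intra-operative leak to persist and no other patient to leak later. The documents do not support that over the looser link, which gives 0.77 and 7% at the same repair rates.
- **7b plans no multivariable analysis of the secondary variable.** That concerns it as an outcome; it does not bar it as a covariate.
- **Overlap with covariate selection.** One prespecified list would answer both points, but the faults differ: a short, fixed model containing further repair has the same bias.

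**Conclusion.** The point holds in conditional form. As worded, 7b lets post-infusion variables into the logistic model. If arm is also in it, the arm odds ratio stops being a randomised comparison. In every no-effect and harm case tried, the shift was towards apparent benefit. Its size ranges from slight to large, depending on detection, the link between intra-operative and later leak, and the screening rule, none of which the documents give. Masking of harm appears under both the loose and the perfect link.

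A reader might conclude that the trial's main result is compromised. It is not: the Fisher test and both risk reductions use no covariates, and harm would still show in the unadjusted leak rates by arm. Nor do the documents show that the investigators intend to adjust for these variables. This is a fault in a supporting analysis, worth closing because closing it costs almost nothing.

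**What to change.** Add to section 7b:

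> Any multivariable model that estimates the treatment effect will contain treatment arm (always retained) and only variables fixed before randomisation (demographics, pre-operative risk factors, operation type and, where recorded separately, closure technique before the infusion). Leak seen, leak site or type, fluid colour, further repair and postoperative variables will not be covariates; they will be analysed as outcomes by arm.

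If the model is meant only to explore risk factors, 7b should say so and state that it gives no treatment-effect estimate.

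The cost is two sentences. No patients are added and the primary test does not change. The one thing to check is whether the CRF records pre-infusion closure technique separately from later revision; if it does not, the wording drops that covariate and needs no new field.
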